4.1.2	Safety Endpoint	7
4.2	Study Duration	7
4.3	Study Assessments	8
4.3.1	Effectiveness Assessment	8
4.3.2	Safety Assessments	9
4.4	Photographs	9
4.5	Study Discontinuation	9
4.6	Investigator Selection	9
5	STUDY POPULATION	9
5.1	Study Subject Recruitment and Selection	9
5.1.1	Inclusion Criteria	9
5.1.2	Exclusion Criteria	10
5.2	Subject Numbering	10
5.3	Subject Discontinuation Criteria	11
6	STUDY PROCEDURES	11
6.1	Measurement Tool	11
6.2	Screening and Enrollment Visit Procedures	11
6.3	4-week and 12-week Follow-Up Visits	13
7	ADVERSE DEVICE EFFECTS	13
7.1	Definitions	13
7.1.1	Adverse Device Effect (ADE)	13
7.1.2	Serious Adverse Device Effect (SADE)	13
7.1.3	Anticipated Serious Adverse Device Effect (ASADE)	13
7.1.4	Unanticipated Serious Adverse Device Effect (USADE/UADE)	15
7.2	Recording Adverse Device Effects	15
7.3	Follow-up of Subjects after ADEs	15
8	POTENTIAL RISKS / BENEFITS	15
8.1	Potential Risks	15
8.2	Potential Benefits	17

8.3 Risk Management.....	17
9 DATA ANALYSIS PLAN.....	17
9.1 Sample Size.....	17
9.2 Analysis Sets	17
9.3 Analysis of Efficacy Endpoints	17
9.3.1 Primary Endpoint Analysis	17
[REDACTED]	
9.4 Safety Analyses.....	18
10 SUBJECT PAYMENT.....	18
11 STUDY MANAGEMENT AND ADMINISTRATIVE PROCEDURES.....	18
11.1 Training and Monitoring.....	18
11.2 Informed Consent.....	18
11.3 Protocol Compliance	19
11.3.1 Protocol Amendments.....	19
11.3.2 Protocol Deviations	19
11.4 Study Personnel.....	19
11.5 Disclosure of Financial Interest	19
11.6 Data Collection, Record Keeping and Storage.....	19
11.7 Subject Confidentiality	20
11.8 Publication Policy	21
REFERENCES	22

[REDACTED]
[REDACTED]
[REDACTED]
[REDACTED]
[REDACTED]

Protocol Summary

Title	Feasibility Study of the TruSculpt Radiofrequency Device
Objective	To evaluate the safety and efficacy of the Cutera truSculpt radiofrequency device for optimal delivery of thermal energy to the skin.
Study Design	A single-center, prospective, open-label study
Enrollment	Up to 40 subjects
Primary Endpoint	
Degree of improvement in the treatment area at 12 weeks post-treatment as assessed by the Investigator.
Safety Endpoint	Incidence and severity of adverse device effects during the study period [REDACTED]
Subject Population	Female and male subjects, age 18 to 70 years, Fitzpatrick skin type I-VI
Planned Schedule	First subject enrolled: January 2017 Last subject last visit: January 2018

1 PURPOSE

The purpose of this investigation is to evaluate the safety and efficacy of the truSculpt radiofrequency (RF) device for optimal delivery of thermal energy to the skin.

2 BACKGROUND INFORMATION

Unwanted excess fat pockets/bulges have been among the top concerns expressed by patients in the aesthetic field. Although surgical interventions produce the most definitive results with body contouring, these invasive methods require significant recovery time and come with inherent risks.

As a non-invasive option, laser, intense pulsed light (IPL), RF, or a combination of these technologies have been developed to reduce skin laxity or fat with minimal recovery time and risks [1]. The tightening effect of the thermal energy generated by these devices has been used for reduction in laxity and fat in areas including but not limited to the face, arms, abdomen, thigh, back and flanks [2-14].

3 STUDY OBJECTIVES

The objectives of this study are to evaluate efficacy and safety of treatment with the Cutera truSculpt RF device for optimal delivery of thermal energy to the skin.

4 STUDY DESIGN

[figure not shown]
This is a single-center, prospective, open-label study in up to 40 subjects, age 18 to 70 years, who desire RF treatment for tissue tightening and/or cellulite reduction. Subjects will receive 1 RF treatment and will be followed at 8 weeks and 12 weeks post-treatment.

4.1 Study Endpoints

4.1.1 Efficacy Endpoints

4.1.1.1 Primary Efficacy Endpoint

- Degree of improvement in the treated area at 12 weeks post-treatment as assessed by the Investigator.

4.1.2 Safety Endpoint

- Incidence and severity of adverse device effects during the study period

4.2 Study Duration

Subjects enrolled in this trial will be asked to participate for approximately 4 months and will complete 4 visits: 1 screening visit, 1 RF treatment visit, and 2 follow-up visits at 8 weeks (\pm 2 weeks) and 12 weeks (\pm 2 weeks) post-treatment.

4.3 Study Assessments

4.3.1 Effectiveness Assessment

4.3.1.1 *Investigator Global Assessment of Improvement*

The investigator will be asked to rate the degree of improvement of the treated area at 12 weeks post-treatment as compared to the subject's baseline photos using the Global Assessment of Improvement Scale:

4 = Very Significant Improvement (> 75%)

3 = Significant Improvement (51 – 75%)

2 = Moderate Improvement (26 – 50%)

1 = Mild Improvement (5 – 25%)

0 = No Change (< 5%)

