5.1.1 Inclusion Criteria

To be included in the study, subjects must meet all of the following Inclusion Criteria:

1.	Male or Female, 18 to 70 years of age (inclusive)
----	---

2.	Fitzpatrick Skin Type I – VI (Appendix 3)
3.	Has visible fat bulges, skin laxity, or cellulite in the treatment area
4.	Non-smoking for at least 6 months and willing to refrain from smoking for the duration of the study.
5.	Subject must agree to not undergo any other procedure(s) in the treatment area during the study period.
6.	Subject must be able to read, understand and sign the Informed Consent Form.
7.	Subject must adhere to the follow-up schedule and study instructions.
8.	Willing to have digital photographs taken of the treatment area and agree to use of photographs for presentation, educational or marketing purposes.
9.	Post-menopausal or surgically sterilized, or using a medically acceptable form of birth control at least 3 months prior to enrollment and during the entire course of the study, and no plans to become pregnant.

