8.2 Potential Benefits

The subjects may or may not benefit from the treatment. Potential benefits include improved appearance of the treated area. There is no guarantee of success.

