11.6 Data Collection, Record Keeping and Storage

The principal investigator is responsible for assuring that all study records including case report forms (CRFs), informed consent forms, device accountability records, source documents (e.g., medical records, histology reports etc.) and other study records are complete, accurate and recorded in a timely manner.

CRFs should not be the only record of a patient's participation in the study and will be used for transcribing data from source documents which are the point of first entry of data collected for each subject (with the exception of documents listed under B). The investigator or research staff at the site will ensure that:

A. Source documentation thoroughly and adequately documented:

1. That patient is participating in a clinical study and has been properly informed and consented prior to participation in the study,
2. Medical history,
3. Concomitant medications,
4. Patient's condition upon entering and during the course of the study,
5. Any adverse event(s) that might have occurred (in addition to the Visit CRFs and/or Adverse Device Effect CRF and/or Cutera SADE form completed),
6. Results of any diagnostic tests/histology conducted during the study.

B. The following data will be recorded directly onto CRFs:

7. Patient meets study inclusion and exclusion criteria,
8. A record of the treatment parameters, including the date of each RF treatment and any other adjunct therapy,
9. Any protocol deviations,

11. Study related improvement assessments by the investigator or investigator's designee,

C. The following documents will be maintained in the study records:

13. The Investigator or the research staff will check signed informed consent for accuracy and will always keep the original copy of the signed informed consent in the CRF binder.
14. All correspondence with an Institutional Review Board (IRB), the sponsor, or FDA including required reports will also be retained in the study records.
15. Records of receipt, use or disposition of the investigational device.

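### Does the primary 0–4 improvement score need redefining because the plan does not say what its percentage measures and words the rater in two ways?

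*Combined protocol and SAP*

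**What the plan says.** The primary endpoint in Section 4.1.1.1, repeated in Section 9.3.1, is "Degree of improvement in the treated area at 12 weeks post-treatment as assessed by the Investigator". Section 4.3.1.1, headed "Investigator Global Assessment of Improvement", puts it into practice. The investigator is to "rate the degree of improvement of the treated area at 12 weeks post-treatment", comparing the area with the subject's baseline photographs and assigning 0 (below 5%), 1 (5–25%), 2 (26–50%), 3 (51–75%) or 4 (above 75%). No anatomical or clinical attribute is attached to the percentage.

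Inclusion criterion 3 in Section 5.1.1 reads "Has visible fat bulges, skin laxity, or cellulite in the treatment area". Section 4 describes subjects "who desire RF treatment for tissue tightening and/or cellulite reduction". One subject may therefore have more than one condition or aim.

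Section 8.2 describes the possible benefit in terms of appearance: "Potential benefits include improved appearance of the treated area".

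In Section 11.6, list B names data entered directly on the CRF. Its item 11 is "Study related improvement assessments by the investigator or investigator's designee". List A of the same section requires source documentation of the patient's "condition upon entering and during the course of the study".

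Section 9.1 caps enrollment at 40 in a feasibility study, and Section 9.3.1 plans a descriptive summary with no formal testing.

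**The concern.** A percentage needs a referent. Fat volume, laxity and cellulite are different quantities, and a device may change one and leave another alone. If a subject has two conditions that respond unequally, the visible text gives no rule for turning two changes into one score. One rater might score the feature that improved most, and another might form an average. Both would enter a number on the same scale, and the pooled distribution would then depend partly on rating habit.

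The rater wording seems to add to this. If a designee may score the primary endpoint, more than one person could be applying a convention that is nowhere written down. The score is also the only efficacy measure visible in the plan, so the descriptive summary would be harder to reproduce and interpret.

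**Working it through.** The plan has no figure to reproduce: no power calculation, effect size or threshold depends on this score. The check is a comparison of the text, followed by an illustration using the scale's own bands.

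**What is rated.** Four features of the text bear on the missing referent:

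- The heading and the name of the scale both call the assessment global.
- The object rated is the treated area, not a named condition.
- The comparator is a set of photographs, which show appearance.
- Section 8.2 states the benefit as a change in the area's appearance.

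Together these point to one overall visual impression of the area against baseline. Scoring only the best feature, or only the worst, is neither global nor a rating of the area.

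**Who rates.** Sections 4.1.1.1, 4.3.1.1 and 9.3.1 all name the Investigator. Item 11 of Section 11.6 adds a designee, but its list says where data are first recorded and does not assign the primary rating. It speaks of assessments in the plural and does not mention the primary score. Parts of the plan are redacted, so other improvement assessments may exist to which the designee wording applies. Section 4 describes a single-center study.

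**How far readings could diverge.** The percentages below are assumptions; only the bands come from Section 4.3.1.1.

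| Change in two conditions | Best feature | Equal-weight average | Other feature |
|---|---|---|---|
| 80%, 0% | 4 | (80+0)/2 = 40% → 2 | 0 |
| 60%, 0% | 3 | (60+0)/2 = 30% → 2 | 0 |
| 40%, 0% | 2 | (40+0)/2 = 20% → 1 | 0 |
| 60%, 40% | 3 | (60+40)/2 = 50% → 2 | 2 |
| 30%, 30% | 2 | (30+30)/2 = 30% → 2 | 2 |

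The average is never less than half the best change, so a best-feature score of 4 (above 75%) implies an average above 37.5%, which scores at least 2. The gap between the best-feature and average readings therefore cannot exceed 2 categories. With one condition the combining question does not arise.

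Suppose k of 40 subjects resembled the 40%/0% row. The share scoring 2 or more would differ between those two readings by k/40:

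- k = 0: 0 points
- k = 4: 4/40 = 10 points
- k = 10: 10/40 = 25 points

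The documents give neither k nor the size of change in any condition. The shift follows entirely from the assumed inputs, and from contrasting two rules that the plan does not contain. It is a what-if, not an estimate.

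**The case for a change.** The strongest case for acting is that the descriptive summary is the whole visible efficacy result, so its meaning should be explicit. Section 8.2 describes benefit and is not a rating instruction. The referent is unstated even for a single condition. The plan uses the designee as a distinct role elsewhere (Sections 11.2 and 11.6) and foresees sub-investigators (Section 11.4). Scores entered directly on the CRF may leave no separate note of how they were reached. One sentence and one harmonised term would cost almost nothing.

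What stands is that the visible text implies overall appearance without stating it, and that item 11 is worded more loosely than the endpoint sections.

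The rest is weaker. A sentence telling the rater to judge all conditions together would write down what a global rating already means. It would still not say how unequal changes become one percentage, which was the original complaint. Nor can it be said that no rating convention exists: the visible steps of the 12-week visit in Section 6.4 contain no improvement rating, several lines there are redacted, and Appendix 1, to which Section 6 refers for the procedures, is not visible. Cheapness alone does not make an editorial preference a defect.

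**Conclusion.** No change follows. The unstated referent is a gap that a rater and an analyst fill sensibly from the text: a global rating of the treated area's appearance against baseline photographs. The rater difference is a looseness of wording in a record-keeping list. It is not a second assignment of the primary assessment.

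Followed as written, the plan gives a sound descriptive summary for an untested, single-center feasibility study. Error rates and power are not at issue, no visible decision threshold depends on the score, and no wrong result has been shown. A global score can still hide unequal change within a subject. That is the ordinary trade-off of such a scale, and stating the referent would not remove it.

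The size of any effect cannot be derived from the documents. The conclusion rests on reading the scale as its name and comparator suggest, and on item 11 not being meant to widen who rates the primary endpoint. Spelling out both would be harmless but optional.

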4.3.2 Safety Assessments

4.3.2.1 *Incidence and Severity of Adverse Events:*

Following the first RF treatment, adverse device effects (ADEs) will be assessed post-treatment and at each subsequent subject visit using the following scale:

- 1= mild: requires minimal or no treatment and does not interfere with the Subject's daily activities.
- 2= moderate: may cause some interference with functioning.
- 3= severe: interrupts Subject's usual daily activity and may require treatment.

4.4 Photographs

Standardized digital photographs will be taken of each subject's treatment area. Photographs will be taken prior to and post all RF treatments, and at each follow-up visit. [REDACTED]

4.5 Study Discontinuation

The study sponsor has the right to terminate this study at any time. Reasons for terminating the study may include, but are not limited to, unsatisfactory subject enrollment or the incidence or severity of adverse events in this study, or other studies with the study device, indicates a potential health hazard to subjects.

4.6 Investigator Selection

Investigators will be invited to participate in the study based on their medical specialty, experience conducting clinical research studies and experience in the use of energy based devices for aesthetic indications. The site's access to potential study subjects and ability to cooperate with study requirements will also be considered.

5 STUDY POPULATION

5.1 Study Subject Recruitment and Selection

Up to 40 male or female subjects, ages 18 to 70, with Fitzpatrick Skin Type I-VI who desire RF treatment will be studied. Subjects will be recruited to participate from those patients who present themselves to the site requesting treatment, or from those patients who respond to advertisement. Only subjects who meet all Inclusion and Exclusion Criteria and provide written informed consent will be enrolled into the study.

Each subject will be evaluated by the Investigator to assess his/her suitability for entry into the study according to the following inclusion and exclusion criteria.

5.1.1 Inclusion Criteria

To be included in the study, subjects must meet all of the following Inclusion Criteria:

1.	Male or Female, 18 to 70 years of age (inclusive)
----	---

2.	Fitzpatrick Skin Type I – VI (Appendix 3)
3.	Has visible fat bulges, skin laxity, or cellulite in the treatment area
4.	Non-smoking for at least 6 months and willing to refrain from smoking for the duration of the study.
5.	Subject must agree to not undergo any other procedure(s) in the treatment area during the study period.
6.	Subject must be able to read, understand and sign the Informed Consent Form.
7.	Subject must adhere to the follow-up schedule and study instructions.
8.	Willing to have digital photographs taken of the treatment area and agree to use of photographs for presentation, educational or marketing purposes.
9.	Post-menopausal or surgically sterilized, or using a medically acceptable form of birth control at least 3 months prior to enrollment and during the entire course of the study, and no plans to become pregnant.

5.1.2 Exclusion Criteria

Subjects will be excluded from the study if they meet any of the following Exclusion Criteria:

1.	Participation in a clinical trial of another device or drug in the target area during the study period.
2.	Has a pacemaker, internal defibrillator, implantable cardioverter-defibrillator, nerve stimulator implant, cochlear implant or any other electronically, magnetically or mechanically activated implant.
3.	Has metal implant(s) within the body that is local to the treatment area, such as surgical clips, plates and screws, intrauterine device (IUD), artificial heart valves or artificial joints.
4.	Significant concurrent illness, such as diabetes mellitus, cardiovascular disease, peripheral vascular disease or pertinent neurological disorders.
5.	Diagnosed or documented immune system disorders.
6.	History of any disease or condition that could impair wound healing.
7.	History of diseases stimulated by heat, such as recurrent herpes zoster in the treatment area, unless treatment is conducted following a prophylactic regimen.
8.	Infection, dermatitis, rash or other skin abnormality in the target area.
9.	Currently undergoing systemic chemotherapy or radiation treatment for cancer, or history of treatment in the target area within 3 months of study participation.
10.	Pregnant or currently breastfeeding.
11.	As per the Investigator's discretion, any physical or mental condition which might make it unsafe for the subject to participate in this study.

5.2 Subject Numbering

Each enrolled subject will be assigned a subject ID number, comprised of the sequential number assigned for each subject treated and the subject initials. The subject initials will be comprised of the first letter of the first and last name.

5.3 Subject Discontinuation Criteria

If possible, every subject should remain in the study until completion of the required follow-up period. However, participation in this study is completely voluntary and a subject can choose to withdraw from the study at any time. In addition, a subject can be discontinued for any of the following reasons: the Principal Investigator decides that continuing in the study would not be in the subject's best interest, a subject is noncompliant with the protocol, a subject has a serious reaction to the treatment, or the study is stopped. In addition, subjects may be discontinued from the study if s/he develops any of the exclusion criteria during the study period. A subject will be considered lost to follow-up only after three unsuccessful, documented attempts to contact the subject have been made. Withdrawn subjects will not be replaced.

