7.2 Recording Adverse Device Effects

All potential ADEs will be evaluated and must be recorded in the subject's medical chart and in the study case report forms. ADEs will be monitored and tracked from the time of the first RF treatment.

At each contact with the subject, the Investigator will seek information on ADEs by specific questioning and, as appropriate, by examination. ADEs may be observed by the Investigator and/or clinical research staff, elicited from the subject and/or family member or volunteered by the subject. All observed and volunteered adverse signs and symptoms (both expected and unexpected), regardless of severity or frequency, will be recorded in the case histories (medical chart and CRFs). Included in the description should be the nature of the sign or symptom, the date of onset, date of resolution (duration), the severity, whether the event was expected or unexpected (anticipated or unanticipated), the relationship to study treatment or other therapy, the action taken (if any), and the outcome.

All SADEs and UADEs must be reported according to Cutera and IRB requirements.

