7.3 Follow-up of Subjects after ADEs

All reported ADEs should be followed until resolution or until the subject's participation in the study ends. Resolutions of such events are to be documented on the appropriate CRF pages. All ADEs that result in permanent discontinuation from this clinical trial, whether serious or not, will also be reported on the Subject Non-Completion of Study Form.

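### With only one RF treatment, discontinuing a treated subject for a device effect also ends follow-up of that effect, so its later course can be lost

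*Combined protocol and SAP*

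**What the plan says.** Section 5.3 opens with a retention default: "If possible, every subject should remain in the study until completion of the required follow-up period". It then lists discretionary reasons for discontinuation. One is that "a subject has a serious reaction to the treatment". Another is that "subjects may be discontinued from the study if s/he develops any of the exclusion criteria during the study period". Exclusion 8 in section 5.1.2 reads "Infection, dermatitis, rash or other skin abnormality in the target area", with no limit on cause or severity. Section 5.3 also says "Withdrawn subjects will not be replaced".

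Section 7.3 sets the end of safety follow-up: "All reported ADEs should be followed until resolution or until the subject's participation in the study ends". It also provides that "All ADEs that result in permanent discontinuation from this clinical trial, whether serious or not, will also be reported" on the non-completion form. Section 7.2 asks that each ADE record include "the date of onset, date of resolution (duration), the severity", along with the outcome.

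The surrounding design is as follows:
- Section 4: one RF treatment, with follow-up at 8 and 12 weeks.
- Section 4.1.2: the safety endpoint is the incidence and severity of ADEs over the study period.
- Section 4.3.1.1: the investigator's improvement rating is made at week 12.
- Section 9.2: the safety set is everyone who starts the session, the efficacy set is everyone who completes it, and missing data are not imputed.

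**The concern.** In a study with repeated treatments, discontinuation can mean stopping treatment while observation goes on. Here there is one treatment, so discontinuing a treated subject can only remove observation. The plan does not separate the two. A device effect may be the reason for leaving, and leaving then closes the record of that effect.

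The subjects who lose follow-up this way would be those with the events that the safety endpoint is meant to describe, so the missing information can be related to the outcome. At stake are how long the effect lasted, how it ended, whether it became worse, and whether another effect followed. There is no formal testing, so the descriptive tables are the study's result, and data not collected by week 12 cannot be recovered by analysis.

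**Working it through.** There is no figure in the plan to reproduce. Section 9.1 gives a cap of 40 subjects without a derivation, and no dropout rate is stated. The check is to follow the rules for one treated subject and then count what is lost.

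**Step 1: the route out.** The direct route is the serious-reaction clause of 5.3. The exclusion-criterion clause is less direct: it reaches device effects only if exclusion 8 is read as covering a local effect that arises after treatment. Its wording allows that reading, and 7.3 itself foresees ADEs that lead to discontinuation without being serious.

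**Step 2: what then stops.** Section 7.3 follows an ADE to resolution or to the end of participation. For an ADE still open at discontinuation, the second limit applies. This is a stated rule and does not depend on redacted text.

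**Step 3: what is kept and what can be lost.**

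| Item | After discontinuation for an ADE |
|---|---|
| Occurrence of the triggering ADE | Kept (7.2, 7.3; safety set in 9.2) |
| Fact of termination due to an ADE | Kept and tabulated (7.3, 9.4) |
| Reporting of a serious or unanticipated effect | Kept under sponsor and IRB requirements that are not shown (7.2; SADE form in 11.6) |
| Resolution date and outcome, if unresolved | Can be lost |
| Peak severity, if the effect later worsens | Can be lost |
| Any later ADE | Can be lost |

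Section 9.4 counts a repeated AE term once, at its greatest severity and longest duration, so the later course bears on the planned table.

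**Step 4: scheduled assessments lost per subject.** Two follow-up ADE assessments are scheduled after the treatment day, at weeks 8 and 12 (4.2, 6.4).
- Exit before the 8-week visit: 2 of 2 lost. No visible visit falls between treatment and week 8, so this needs exit on the treatment day or at an unscheduled contact.
- Exit at the 8-week visit: 1 of 2 lost. That visit's ADE record and photographs exist.

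**Step 5: the week-12 rating (secondary, inferred).** A subject who has left the study would probably not be rated at week 12. This is inferred from leaving the study; 7.3 does not govern the rating. It applies only to subjects who completed the session, since others are outside the efficacy set. For each missing rating among n such subjects, the gap between the worst and best case is:
- proportion at any cut-off: 1/n
- mean on the 0 to 4 scale: 4/n

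| n | 1/n | 4/n |
|---|---|---|
| 40 (stated maximum) | 1/40 = 2.5 points | 4/40 = 0.10 |
| 30 (assumed) | 1/30 = 3.3 points | 4/30 = 0.13 |
| 20 (assumed) | 1/20 = 5.0 points | 4/20 = 0.20 |

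Because 40 is a cap, the first row is the minimum. The widths assume a summary over all subjects in the efficacy set; the form of the planned summary is not visible.

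**The case against.** The strongest reply is that the plan clearly expects subjects with ADEs to stay. Section 5.3 starts from retention, its triggers are discretionary, and sections 4.3.2.1 and 6.4 provide for ADE assessment at both follow-up visits. Nothing shows that ordinary local effects lead to exit. This stands as a limit on how often the problem will arise. It does not say what is collected once the discretion has been used.

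Second, the event is not hidden. It is recorded, entered on the non-completion form and tabulated, and serious effects go through separate reporting. This also stands. A reader might infer that the triggering ADE drops out of the safety tables, or that serious effects go unfollowed. The documents do not support the first, and the second cannot be judged because the sponsor and IRB requirements are not shown.

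Third, Appendix 1 and parts of 6.3, 6.4 and 9.4 are not visible, so an exit assessment may exist. One cannot be ruled out, and the point does not claim that none exists. An assessment at exit would still not supply the course of the effect after exit, or a week-12 rating.

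Fourth, the 1/n and 4/n figures apply to any missing rating from any cause. That is correct. They show the effect of one loss and do not estimate how many losses there will be.

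Fifth, a rule that kept every discontinued subject in scheduled visits would cut into the investigator's best-interest judgement, because only visits remain after treatment. This stands, and the proposed change leaves that judgement intact.

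**Conclusion.** The concern holds in a limited form. Sections 5.3 and 7.3 do not contradict each other, but in a one-treatment study their joint effect is that a treated subject discontinued for a device effect can lose the resolution date, the outcome, possibly the peak severity, and any later ADE. One or both of the two scheduled follow-up ADE assessments go. The occurrence of the triggering effect is kept. The number of subjects affected is unknown, cannot be derived from the documents and may be zero.

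Loss of the week-12 rating is a probable secondary consequence, worth 2.5 points or 0.10 on the scale per missing rating at 40 subjects and more with fewer.

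Three stronger readings are tempting and not supported:
- **That 5.3 requires removal for any rash.** The wording is permissive.
- **That durations will come out too short.** The duration of an ADE open at exit is unknown, and how open events are summarised is not visible.
- **That the efficacy summary will be too favourable.** That would follow only if the missing subjects had poor ratings, and the documents give no basis for a direction.

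This is a change worth making because it is cheap and the data cannot be collected afterwards. Confidence is medium, given the redactions.

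**What to change.** State in 7.3, with a cross-reference in 5.3, that for a subject who has started the RF session, discontinuation for a serious reaction, another ADE or a newly met exclusion criterion does not by itself end recording of ADEs through the already scheduled 8- and 12-week time points. Add that the week-12 photographs and investigator rating are still collected where the subject agrees. Follow-up stops if the subject declines it or the study is stopped. If Appendix 1 contains an exit assessment, refer to it.

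The change concerns data collection only. The reasons for discontinuation stay as they are, and so does the investigator's best-interest judgement, including whether visits are appropriate for that subject. Any later procedure or treatment in the treated area should be reported alongside the rating, since it may affect it.

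The cost is a sentence or two in 7.3 and a cross-reference in 5.3, made by written amendment signed by the sponsor and the principal investigator, with IRB approval (11.3.1). The consent wording must be aligned with section 11.7, which speaks of information collected up to the time of withdrawal. No new visits are created: at most the two already planned are kept for each subject concerned. The downside is that a few discontinued subjects attend those visits and some of their ratings may reflect later treatment.
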